12.1.4 Secondary Analysis

For both Cohort 0+A combined and Cohort B progression free survival (PFS) will be defined as the time from date of study treatment to the time of first observed disease progression (modified RECIST 1.1 criteria) at the treated tumor site or death due to any cause. PFS will be summarized using standard Kaplan-Meier methods, with median PFS and specified PFS rates estimated with 95% confidence intervals. The number of bronchoscopies will be summarized descriptively.

For Cohort A only we will measure agreement between DOSIETM and COMSOLTM treatment planning measures in n=18 subjects consisting of light intensity from each fiber (mW, and mW/cm), percent of tumor that receives ≥ 8.6 mW/cm² and ≥ 45 J/cm², the irradiance and fluence at the margins, the min, average and maximum irradiance and fluence in 100% of the tumor using the concordance correlation coefficient (76)(CCC) and Bland-Altman plots (77) for visual displays of agreement. We will calculate the one-sided 95% confidence interval for the CCC using a percentile bootstrap-t approach for each endpoint and we will calculate the 95% confidence interval display. Disagreement on a given measure will be inferred if the estimated CCC is below the lower bound of the one-sided 95% percentile confidence interval.

Tumor response as a function of STAT3 tumor conversion percentages (if possible) will be analyzed using logistic regression adjusted for age and sex.

The data from this trial will inform the design of a prospective Phase IIb randomized trial.

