4.1.3 Secondary Endpoints (Cohort A and Cohort B)

- The number of bronchoscopies
- Evaluate progression free survival (PFS)
 - Compare the treatment planning in DOSIETM with the plan generated in COMSOLTM in Cohort A only.
- To measure changes in tumor pO2, optical properties, and irradiance and fluence in relationship to response.

All participants will sign an informed consent prior to study related tests and interventions. All participants will meet the inclusion and exclusion criteria summarized in Section 5.1 and Section 5.2.

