4.1.4 Target Accrual and Study Duration

Eight patients in the Phase I (Cohort 0), and 18 patients will be enrolled in the Phase II Cohort A (8 already enrolled under Phase 1 portion of Cohort A from previous protocol version) and 39 in Cohort B (65 patients total). It is expected to have up to 32 patients enrolled from accompanying external sites and the remainder enrolled from Roswell Park. Accrual is expected to take up to 10 years.

Patients will be drawn from the interventional pulmonology practice and from referrals from medical oncologists. All patients will come off study at 24 weeks.

Enrolled patients who do not receive the I-PDT and/or PDT for any reason (such as patient withdrawal, safety or inability to deliver the I-PDT) will be replaced.

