8.1.8 Initial Follow-Up Evaluation

The following evaluations will be performed **4 weeks** (± **1 week**) after the last study I-PDT and/or PDT (*unless otherwise indicated**):

- Physical examination (including vital signs)
- Hematology: Complete blood count (CBC) with automated differentials.
- Chemistry: Complete metabolic panel (CMP).
- Blood draw for immune markers
- ECOG Performance Status (Appendix A)
- Tumor/Disease Assessment: Chest CT scan
- Concomitant medications
- Quality of Life Questionnaire (Cohorts A and B; Appendix D)
- Adverse events (will be followed for 30 days following treatment/procedure)
- Schedule date/time for follow-up bronchoscopy with EBUS (without TBNA). TBNA will be performed only if clinically indicated outside the scope of this study. If a tumor is visible, tumor tissue biopsies (about 50-300 mg per biopsy, if feasible) will be collected for immune markers. NOTE: The bronchoscopy will not be performed at this visit.
- If EBUS is performed and a tumor is visible, tumor tissue biopsies (about 50-300 mg per biopsy, if feasible) will be collected for immune markers.

*Bronchoscopic and ultrasound images that are routinely obtained during therapeutic procedures will be used to evaluate the airway initially and during follow up. *Note: Initial follow-up bronchoscopy will be performed within 4 weeks following the first follow-up visit. Additional bronchoscopies will be performed as clinically indicated.*

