8.1.9 Long Term Follow-Up Evaluations

The following evaluations will be performed at 8 weeks (± 2 weeks), 12 weeks (± 2 weeks) and 24 weeks (± 4 weeks) after last study I-PDT and/or PDT (or when clinically indicated):

Physical examination (including vital signs)

ECOG Performance Status (Appendix A)

Concomitant medications: Required as indicated throughout the long-term follow-up period so that any medications that may interfere with immune function are documented.

Chest CT scan

Quality of Life Questionnaire at 12 and 24 weeks (Cohorts A and B; Appendix D)

Six-Minute Walk Test at 12 weeks and 24 weeks (Cohorts A and B)

8.1.10 Patients coming off the study:

• Patients will be taken off the study and no data will be collected after the follow-up visit at 24 weeks (± 4 weeks) after the last I-PDT and/or PDT.

• All patients, including those that progress prior to 24 weeks, will continue to be followed for disease and survival status for the full 24 weeks.

Progression of disease will not cause the patients to be off study. We will continue to collect response data as it will be part of standard of care for these patients. We will use modified RECIST 1.1 to determine response.

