12 STATISTICAL METHODOLOGY

This is a multi-center, multi-arm, Phase I (Cohort 0, data collection completed) and Phase II study [Cohort A (8 already enrolled under Phase 1 portion of Cohort A from previous protocol version) and Cohort B]. Cohort 0 is closed to accrual and fulfilled the Phase 1 safety monitoring requirements. Cohort 0 provided the safety monitoring component for Cohort A of this Phase II study. Cohort 0 consisted of patients with the diagnosis of lung cancer that received porfimer sodium with EBUS I-PDT and all of the study procedures with the exception of the Quality of Life Questionnaires and Six Minute Walk Test. Cohort A consists of patients with the diagnosis of lung cancer or other malignancies causing airway obstruction, or cancer that is not a candidate

for surgery or curative radiation therapy; EBUS I-PDT; and all of the study procedures. Cohort B will consist of patients with the diagnosis of lung cancer or other malignancies causing airway obstruction, or cancer that is not a candidate for surgery or curative radiation therapy. Subjects in Cohort B will receive the EBUS guided I-PDT 48 ± 4 h after standard of care palliative radiotherapy of 8 Gy x1.

The primary safety endpoints for Cohort 0 for this study are:

• AEs that are \geq Grade 4.

The primary efficacy endpoints for Cohort A and Cohort B portion of this study are:

- Objective tumor response (CR, PR, PD, and SD)
- The FACT-L Total Score related subscale
- 6-Minute walk measures

The secondary endpoints for Cohort 0+A and Cohort B of this study are:

- The number of bronchoscopies
- Progression free survival
- Compare the treatment plan in DOSIE[™] with the plan generated in COMSOL[™] in Cohort A only.
- Measure changes in optical properties and irradiance and fluence and relationship to response.

The exploratory endpoints are for Cohort 0+A and Cohort B of this study:

- Porfimer sodium retention in the target tumor tissue
- The relationship between immune biomarkers and response

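### The number of bronchoscopies is summarised with no time-at-risk denominator and no handling of death, so the figure reflects survival and retreatment as well as need for procedures

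*Combined protocol and SAP*

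**What the plan says.** Section 4.1.3 lists "The number of bronchoscopies" as a secondary endpoint without saying when counting starts or which procedures qualify. Section 12 repeats it under the line "The secondary endpoints for Cohort 0+A and Cohort B of this study are", so it is reported once for Cohort 0+A and once for Cohort B. The analysis in Section 12.1.4 is: "The number of bronchoscopies will be summarized descriptively".

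On observation time, Section 4.1.4 says "All patients will come off study at 24 weeks". Section 8.1.10 is more specific: "Patients will be taken off the study and no data will be collected after the follow-up visit at 24 weeks", with a ± 4 week window, counted from the last I-PDT and/or PDT. Patients who progress early "will continue to be followed for disease and survival status for the full 24 weeks", so progression does not shorten observation, but death does.

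Several kinds of bronchoscopy could enter the count:
- the Day 0 treatment procedure;
- a bronchoscopy at 48 ± 4 hours if clinically indicated, possibly with further I-PDT (Section 8.1.6);
- retreatment light sessions at the physician's discretion (Section 6.1.4);
- a scheduled one: "Initial follow-up bronchoscopy will be performed within 4 weeks following the first follow-up visit" (Section 8.1.8);
- any others: "Additional bronchoscopies will be performed as clinically indicated" (Section 8.1.8).

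Section 4.1 times the repeat bronchoscopy differently, at four weeks (± 2 weeks) after the intervention. The two passages need to be reconciled.

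**The concern.** The Rationale (Section 2) presents repeated palliative bronchoscopies as a burden of this disease, and the stated hypothesis is a longer palliation period. A reader will naturally take a low number as good. But the patients are described there as being at a terminal stage, and ECOG status up to 3 is eligible, so some will probably die before 24 weeks. A patient who dies at week 6 can have few bronchoscopies simply because there was little time in which to have them.

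Two further features distort the count. Because the clock runs from the last treatment, a retreated patient is observed for longer and also contributes the retreatment session. And a protocol-scheduled procedure says nothing about need, yet early death can remove it. In the same section, PFS counts death as an event, while the bronchoscopy count has no corresponding rule.

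At stake is the usefulness of a descriptive figure: its plain reading, the side-by-side reading of the two cohorts, and its use in the Phase IIb randomised trial that Section 12.1.4 says these data will inform.

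**Working it through.** The plan states no rate, expected count, power or sample size for this endpoint, so there is no figure to reproduce. The steps below only gauge how far a count and a rate can part.

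**Inputs from the documents.** Observation to 24 weeks (± 4) after the last treatment; one scheduled follow-up bronchoscopy by about week 8 (the week-4 visit plus up to 4 weeks); progression does not end observation.

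**Inputs assumed.** 24-week mortality m from 10% to 70%; exponential survival; 1 or 2 bronchoscopies per 24 weeks alive. Section 1.1.10 reports 3 of 10 earlier patients alive at 8.3, 12 and 26.5 months, which does not give 24-week mortality.

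**Step 1: constant need.** With h = −ln(1 − m), the mean share of the 24 weeks spent alive is (1 − e^(−h))/h = m/h. The mean count is the rate times this share. For m = 40%, h = 0.511 and 0.40/0.511 = 0.783.

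| 24-week mortality | h | Mean count, rate 1 | Mean count, rate 2 | Below the rate by |
|---|---|---|---|---|
| 10% | 0.105 | 0.949 | 1.90 | 5.1% |
| 20% | 0.223 | 0.896 | 1.79 | 10.4% |
| 40% | 0.511 | 0.783 | 1.57 | 21.7% |
| 60% | 0.916 | 0.655 | 1.31 | 34.5% |
| 70% | 1.204 | 0.581 | 1.16 | 41.9% |

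Events divided by person-time return the true rate in every row.

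**Step 2: two cohorts with the same need.** If one cohort had 20% mortality and the other 40%, their mean counts would be 0.896 and 0.783, a ratio of 0.783/0.896 = 0.87. The second would look 13% lower with identical need.

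**Step 3: need that rises before death.** Let patients who die have k times the rate. At m = 40%, survivors contribute 0.60 × 1 and those who die contribute (0.783 − 0.600) × k = 0.183k. The mean count is 0.600 + 0.183k: 0.78, 0.87, 0.97 and 1.15 for k = 1, 1.5, 2 and 3, against 1.0 in survivors. The shortfall vanishes at k = 0.400/0.183, about 2.2, and reverses above that. At k = 2 the count of 0.97 is almost the survivors' value, while the rate per 24 weeks alive is 0.966/0.783 = 1.23. There the count hides the higher need.

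**Step 4: the scheduled procedure.** At m = 40%, the proportion alive at week 8 is 0.60^(8/24) = 0.843. Adding one scheduled bronchoscopy gives 0.783 + 0.843 = 1.626, against 2 with no deaths, or 18.7% lower. Mixing in scheduled procedures changes the size of the distortion without removing it.

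**Step 5: survivors.** The visit window alone spans 20 to 28 weeks. At 1 per 24 weeks, that gives 20/24 = 0.83 to 28/24 = 1.17. A retreatment w weeks after the first treatment extends time on study from 24 to 24 + w weeks and adds a procedure; the documents set no limit on w.

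**The case against.** The strongest reply is that the plan claims little here. The endpoint is descriptive, with no hypothesis, control, historical rate or test. The secondary objectives in Section 3.1.3 do not mention bronchoscopies, and Section 12 plans no between-cohort comparison of them. A reader might infer that early deaths will make the treatment appear to reduce repeat procedures. The documents do not support that, because an apparent reduction needs something to be reduced from and the plan names no reference. This part of the objection stands, and it confines the issue to interpretation and reuse.

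The wording also does not commit to a bare count over a fixed 24 weeks. A descriptive summary could include follow-up time or a rate. That is fair, but nothing in the plan requires it, and a count is the natural reading of an endpoint defined as a number.

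The direction is not assured either. Step 3 shows that the shortfall can disappear or reverse if need rises before death. This stands too, but it also favours showing person-time and deaths, since the count alone cannot tell the two situations apart.

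Finally, PFS with death as an event and survival status to 24 weeks will be reported, so heavy early mortality would be visible elsewhere. That helps an attentive reader but does not yield a rate.

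**Conclusion.** The point holds as a minor one. Analysed as written, the number of bronchoscopies combines need, survival, length of follow-up and retreatment, and the plan offers no way to separate them. Under a constant rate and exponential survival, the mean count is about 5% to 42% below the rate per 24 weeks alive for 24-week mortality of 10% to 70%. The mortality, the rate and the constancy are assumptions, so this range is an illustration and not an estimate for this trial. Whether a cohort with more deaths shows a lower count depends on how need changes before death. No alpha, power, sample size or decision rule is affected.

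**What to change.** In Section 12.1.4, keep the count and add, for Cohort 0+A and for Cohort B:
- bronchoscopies after the first study treatment (excluding the Day 0 procedure) per patient-month alive on study, with an overdispersion-robust 95% interval;
- the number of deaths and the total person-time;
- protocol-scheduled follow-up and retreatment bronchoscopies shown separately from clinically indicated ones, with a statement of where the 48-hour procedure belongs;
- preferably, a mean cumulative function with death as a terminal event, because a pooled rate does not show how need changes as death approaches.

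The cost is some SAP wording and a little extra analysis. One thing must be checked first. Survival status is collected to 24 weeks, but the documents do not show that the date and indication of each later bronchoscopy are recorded, and note 10 to Table 1 says details of the standard-of-care interventional procedure need not be entered in the case report form. If they are not captured, a short data field is needed.

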- o At [name] laboratory, both DOSIE[™] and COMSOL[™] will be used to generate treatment planning for 630-nm laser. Each plan will use the same number and location of the fiber placement, diffuser length, and intensity (W/cm). The software packages will be used to compute the irradiance and fluence required to administer our target irradiance of ≥ 8.6 mW/cm² in a significant volume of the target tumor. The plans will also suggest the treatment time to deliver ≥45 J/cm² to a significant volume of the target tumor.
- For each plan, the research team will generate a table showing the light delivery options and percent of tumor volume that will receive the minimal and maximal irradiance and fluence for the physician to review.
- The research team will compare the DOSIETM computation with the COMSOLTM. Although both use same input, the differences in the mesh generation and the solvers used in the simulations could impact the resulted irradiance and fluence. The comparison will include percent of tumor that receive ≥ 8.6 mW/cm² and ≥ 45 J/cm², the irradiance and fluence at the margins, the minimum, average, and maximum irradiance and fluence in 100% of the tumor. If there is disagreement (more than 5% difference) we will use COMSOLTM computation.
- The treating physician will review the plan and either approve or request changes.
 - Several iterations (typically 1-3) may be required until the treating physician approves the plan. The review will be in-person or via secured web-based communication (e.g., password protected Microsoft Teams).
 - Once approved, a detailed description of the plan will be provided via secured e-mail.
- The I-PDT procedure will follow the plan as much as possible, taking into consideration patient safety, and treatment time.
 - \circ Our previous studies suggest that fiber placement within ≤ 10 mm from the planned placement will have insignificant impact on the total light irradiance and fluence in the target tumor.

• The difference between the planned and actual placement of the fibers will be recorded (using EBUS imaging and measurements). These data will be used for post analysis, to calculate the actual light distribution by DOSIE[™] and COMSOL[™].

Extrabronchial tumors that are identified by EBUS will be treated with I-PDT. The laser fiber will be inserted into the tumor using the EBUS-TBN. The I-PDT procedure will follow these steps:

- Curvilinear Endobronchial Ultrasound will be used to identify the tumor.

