12.1.3 Primary Phase II Efficacy Analysis

The primary endpoint for Cohort A and Cohort B is the proportion of complete responders (CR) and partial responders (PR) as measured by RECIST v1.1 at 12 ± 1 week after DOSIETM (Cohort A) and COMSOLTM guided I-PDT.

For Cohort A, we hypothesize that the objective tumor response for CR+PR will be at least 29%. We also want to investigate the impact of variation in optical properties, Photofrin® retention, and fiber location perturbation on the objective tumor response. The primary analysis will consist of a one-sided exact binomial test of H₀: π =0.05 versus H_a: π >0.05 at level α =0.05, where π is the proportion of CR+PR responders. For Cohort B, the primary analysis will consist of a one-sided exact binomial test of H₀: π =0.30 versus H_a: π >0.30 at level α =0.05.

Additional clinical efficacy endpoints are: (1) changes from baseline to 3 months in the FACT-L Total Score related subscales (physical well-being, social/family well-being, emotional well-being, functional well-being); (2) the 6-minute walk measures (distance, VO2max, shortness of breath scores). All key clinical efficacy outcomes will be considered suitably continuous will be analyzed with an analysis-of-covariance (ANCOVA) approach regressing change from baseline to three months on the baseline value of the respective measure adjusted for baseline tumor volume, age, and sex.

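### DOSIE–COMSOL agreement is assessed on per-fibre light intensity, which Section 6.1.2 makes a shared input, and not on planned treatment time, which can differ

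*Combined protocol and SAP*

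**What the plan says.** - Section 12.1.4 plans CCCs and Bland-Altman plots for Cohort A on "treatment planning measures in n=18 subjects consisting of light intensity from each fiber (mW, and mW/cm". It also lists the percent of tumour above the irradiance and fluence thresholds, irradiance and fluence at the margins, and their minimum, average and maximum over the tumour.
- Section 6.1.2 fixes what goes into the two plans: "Each plan will use the same number and location of the fiber placement, diffuser length, and intensity (W/cm". It explains where they may part: "Although both use same input, the differences in the mesh generation and the solvers used in the simulations could impact the resulted irradiance and fluence".
- Section 6.1.2 has its own comparison list, which begins "The comparison will include percent of tumor that receive ≥ 8.6 mW/cm² and ≥ 45 J/cm², the irradiance and fluence at the margins" and continues with the minimum, average and maximum. Intensity is not on it.
- Section 6.1.2 names a further output of each plan: "The plans will also suggest the treatment time to deliver" at least 45 J/cm² to a significant volume of the tumour. Time is on neither list.
- Section 6.1.2 sets a fallback: "If there is disagreement (more than 5% difference) we will use COMSOLTM computation". Section 12.1.3 times the primary endpoint "at 12 ± 1 week after DOSIETM (Cohort A) and COMSOLTM guided I-PDT" and does not mention the fallback. The treatment table in Section 6 names both planning systems for Cohort A and only the in-house one for Cohort B.

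**The concern.** An agreement analysis is informative only on quantities that the two methods produce separately. Per-fibre intensity is a setting given to both packages, so agreement on it says nothing about either one. Treatment time is something each package suggests, and with fibre number, position, diffuser length and intensity fixed it is the delivery parameter left to be set. The secondary objective could thus show agreement on two measures where disagreement is impossible, and say nothing directly about one where it is possible. Section 1.1.9 presents the testing of DOSIE as a significant part of the study and mentions a long-term aim of regulatory approval, so agreement that comes from shared inputs should not be counted as evidence.

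The secondary issue is descriptive. A reader of Section 12.1.3 alone cannot tell which computation was used to treat a given Cohort A patient, and the plan does not ask for the number treated on COMSOL because of the 5% rule.

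**Working it through.** **1. The plan's own figure.** The agreement analysis has no sample-size basis of its own. Its n=18 is the Cohort A number from Section 12.1.6, chosen for the response test (null 0.05, alternative 0.29, one-sided α 0.05, power 0.80). By the exact binomial with n=18, P(X≥3 | 0.05) = 0.0581, which is too large, and P(X≥4 | 0.05) = 0.0109. The rule is therefore at least 4 responders, with power P(X≥4 | 0.29) = 0.812. The stated 0.80 reproduces, and nothing below changes it.

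**2. The intensity pairs.** Let x be the DOSIE value and y the COMSOL value for a patient.
- mW/cm: x = y, by Section 6.1.2. The Figure 3 legend in Section 1.1.9 likewise treats 400 mW/cm as an input.
- mW: power = intensity × diffuser length, and both factors are shared. In the Figure 3 example, 400 mW/cm × 4 cm = 1,600 mW in either package.

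**3. CCC and Bland-Altman on identical pairs.** CCC = 2·s_xy / (s_x² + s_y² + (x̄ − ȳ)²). With x = y, s_xy = s_x² = s_y² = s² and the mean difference is 0.
- If the setting varies between patients (s² > 0): CCC = 2s²/2s² = 1.
- If every patient has the same setting (s² = 0): CCC = 0/0, undefined.
- In both cases every Bland-Altman difference is 0.

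Numerical check with 18 pairs. Settings drawn between 100 and 400 mW/cm gave numerator and denominator both 12,736.1, so CCC = 1.000. Multiplying by diffuser lengths of 1 to 4 cm gave 209,010.5 / 209,010.5 = 1.000. All 2,000 bootstrap resamples of the mW/cm pairs gave 1.000, and the SD of their differences was 0. With 400 mW/cm in every patient the result was 0/0.

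**4. Why treatment time can differ.** At a point in the tumour, fluence = irradiance × time. Suppose one package computes an irradiance higher by a fraction d at the location that governs the plan. If time is held common, its fluence is higher by d. If each package sets its own time to reach 45 J/cm², its time is multiplied by 1/(1+d) and both plans report 45 J/cm² there. Illustration (assumed d = 5%, single location, at the 8.6 mW/cm² threshold): 45/0.0086 = 5,233 s against 45/(0.0086 × 1.05) = 4,983 s. That is 249 s or 4.8% shorter, with no difference in fluence at that point. The sections do not say whether fluence is compared at a common time.

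**5. How often the 5% rule might apply.** The documents give no between-package differences, so this is purely an assumption: relative difference ~ N(0, s), with k independent measures each checked against 5%. Then p = 2(1 − Φ(0.05/s)), and the expected number of patients is 18·(1 − (1 − p)^k).

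| s | k = 1 | k = 2 | k = 10 |
|---|---|---|---|
| 1% | 0.0 | 0.0 | 0.0 |
| 2% | 0.2 | 0.4 | 2.1 |
| 3% | 1.7 | 3.3 | 11.4 |
| 5% | 5.7 | 9.6 | 17.6 |
| 10% | 11.1 | 15.4 | 18.0 |

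The range runs from none to all of Cohort A, and depends heavily on how many measures the rule covers, which is not stated.

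**The case against.** **Treatment time is already covered indirectly.** With shared inputs, a difference in suggested time must come from a difference in computed irradiance, and irradiance is compared at the margins and as minimum, average and maximum. This largely stands: a solver difference would not go unseen. It does not show how that difference carries into the time each plan suggests, and the fluence measures may hide it if each package uses its own time.

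**The impact is small.** This is a secondary software comparison, a row of zeros is easy to recognise, and every other listed measure can genuinely differ. That stands, and it limits the point to a weakness in the objective.

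**Stronger readings that a reader might infer, and that the documents do not support:**
- That Cohort A is presented as treated on DOSIE alone. Section 12.1.3 names DOSIE for Cohort A and also COMSOL. Read with the Section 6 table, it can mean planning with both packages. What remains is that the fallback is not mentioned there.
- That no DOSIE plan differing by more than 5% can ever reach a patient. The rule names neither the measure nor the denominator, so a plan could meet it on one measure and exceed 5% on another. Zero cannot be derived.
- That the CCC will always be exactly 1. It is undefined if all patients share one setting.
- That the comparison might be made only after physicians have revised the plans. Section 6.1.2 already lists it before physician review.

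**Conclusion.** The point holds as an inconsistency between Sections 12.1.4 and 6.1.2 with a specific omission. Two of the listed agreement measures, mW and mW/cm, are degenerate by design: CCC 1 or undefined, all differences 0. Planned treatment time, which each package outputs, is not compared. This rests on taking Section 6.1.2 at its word that intensity and diffuser length are the same in both plans. If the sponsor instead means each package to choose its own intensity, Section 6.1.2 is the text that must change.

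The Cohort A wording is a secondary matter of reconciliation and reporting, and its size cannot be determined from the documents. The remaining agreement measures, the primary response test, its power (0.812 exact) and n=18 are unaffected.

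**What to change.** - In Section 12.1.4, remove per-fibre light intensity (mW and mW/cm) from the agreement measures, or report it only as a shared input. Add planned treatment time to reach at least 45 J/cm², per fibre or in total. Keep the other measures.
- Reconcile the Section 6 treatment table, Section 6.1.2 and Section 12.1.3 on how the two packages are used in Cohort A. State which measure, and relative to what, the 5% rule applies to. Report how many Cohort A patients were treated on the COMSOL computation because of it. Which rule should govern treatment is for the sponsor to decide.

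The cost is wording and one count. Each plan already produces treatment time, so no new planning data are needed, but the computation used must be recorded for each patient. What is lost is two measures that could not have shown disagreement.

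### The DOSIE–COMSOL agreement analysis is not tied to the protocol's 5% limit: the concordance correlation cannot show whether that limit was met, and its disagreement rule would practically never fire

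*Combined protocol and SAP*

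**What the plan says.** Section 6.1.2 (EBUS and Light Delivery for I-PDT) has both packages compute a plan for the same patient from the same fiber number, fiber positions, diffuser length and intensity. The results compared are the share of the tumor reaching the irradiance and fluence targets, and "the irradiance and fluence at the margins, the minimum, average, and maximum irradiance and fluence in 100% of the tumor". A tolerance follows: "If there is disagreement (more than 5% difference) we will use COMSOLTM computation". The section does not say which of these measures triggers the rule. Nor does it say whether 5% is relative or in percentage points for measures that are already percentages.

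Section 12.1.4 (Secondary Analysis) covers the Cohort A secondary objective of comparing the two plans in 18 subjects. It lists largely the same measures, adds light intensity from each fiber, and assesses agreement "using the concordance correlation coefficient (76)(CCC) and Bland-Altman plots (77) for visual displays of agreement". For inference it says: "We will calculate the one-sided 95% confidence interval for the CCC using a percentile bootstrap-t approach for each endpoint". The decision rule is: "Disagreement on a given measure will be inferred if the estimated CCC is below the lower bound of the one-sided 95% percentile confidence interval".

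Section 12.1.4 contains no reference to the 5% limit, no minimum acceptable CCC, no acceptance limits for the Bland-Altman plots, and no count of plans that exceeded 5% or were overridden.

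**The concern.** The two sections define disagreement on different scales. Section 6.1.2 works on the percentage difference within one patient's plan. The CCC divides the disagreement by a quantity dominated by how much patients differ from one another. The same software error can then give a high or a low CCC depending on the mix of tumors enrolled, although the number of plans beyond 5% is unchanged.

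A reader shown a CCC of, say, 0.97 would take it as good agreement and could not tell how often the DOSIE computation had been set aside. The result is likely to be used: Section 12.1.4 says the trial's data will inform a randomized Phase IIb design, and Section 1.1.9 records that the developer's long-term aim is FDA approval of DOSIE.

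The decision rule raises a separate difficulty. It asks whether an estimate lies below the lower bound of what reads as the confidence interval built around that same estimate. A meaningful rule would compare the bound with a fixed external value.

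**Working it through.** **Plan's own figure.** There is none to reproduce for agreement: no target CCC, expected CCC or precision is stated. The 18 is the Cohort A response sample size (Section 12.1.6). With rejection at 4 or more responders, the exact binomial gives alpha 0.011 at a 5% response rate and power 0.81 at 29%, in line with the stated 0.80. It was not derived for the agreement question.

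**Inputs.** From the documents: 18 paired plans, the CCC, the one-sided 95% bound and the 5% limit. Assumed, because not given: the between-patient CV (5% to 100%) and the size and pattern of the DOSIE–COMSOL difference, taken relative to COMSOL.

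**Step 1: uniform shift.** The CCC is 2s_xy / (s_x² + s_y² + (mean_x − mean_y)²). If DOSIE = (1 + d) × COMSOL and c is the between-patient CV, then

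CCC = 2(1 + d)c² / {[1 + (1 + d)²]c² + d²}.

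For d = 0.10 and c = 0.10: 0.0220 / (0.0221 + 0.0100) = 0.685. For c = 0.50: 0.5500 / (0.5525 + 0.0100) = 0.978.

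| Between-patient CV | CCC, 5% shift (at the limit) | CCC, 10% shift (twice the limit) |
|---|---|---|
| 5% | 0.677 | 0.354 |
| 10% | 0.893 | 0.685 |
| 20% | 0.970 | 0.894 |
| 30% | 0.986 | 0.948 |
| 50% | 0.994 | 0.978 |
| 75% | 0.997 | 0.988 |
| 100% | 0.998 | 0.991 |

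A shift exactly at the limit corresponds to anything from 0.68 to 0.998. No single CCC value stands for 5%.

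**Step 2: samples of 18.** In 20,000 simulated sets per setting (lognormal measure; percentage difference normal, mean 10%, SD 2%), 99.4% of plans exceed 5% at every CV. The median CCC (5th to 95th percentile) is:

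- CV 10%: 0.65 (0.50–0.77)
- CV 20%: 0.88 (0.79–0.93)
- CV 30%: 0.94 (0.89–0.97)
- CV 50%: 0.97 (0.95–0.99)

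With SD 3%, 95% of plans exceed the limit and the CCCs are almost the same. With purely random differences (mean 0, SD 10%), the CCCs are again similar, but only 62% of plans exceed 5%.

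**Step 3: bounded measures.** For a percent-of-tumor measure spread evenly over 80–100% (CV about 6%), a 10% shortfall gives a median CCC of 0.40. Over 60–100% it is 0.77, and over 20–100% it is 0.96.

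**Step 4: the percentage scale.** In the step 2 setting (mean 10%, SD 2%), the limits of agreement are 10 ± 1.96 × 2, or 6.1% to 13.9%. The 95% CI for the mean with n = 18 is 10 ± 2.11 × 2/√18, or 9.0% to 11.0%. Both lie wholly above 5%, whatever the CV.

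**Step 5: the decision rule.** The rule was simulated with both a percentile and a bootstrap-t lower bound, 150 data sets in each of five scenarios. Disagreement was inferred in 0 of 150 in every scenario, including two with a 50% bias.

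**The case against.** The case for leaving the plan alone has real content.

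- **The CCC is not blind in general.** At a CV of 20% or less, a 10% shift lowers it to 0.89 or below, and percent-of-tumor measures clustered near 100% would show plain disagreement. No between-patient CV is documented. This stands, and it limits the point to dependence on spread.
- **The Bland-Altman plots would show a 10% shift.** They would, by eye. An unclear clause in Section 12.1.4 about a 95% confidence interval for a display may even mean intervals on those plots. But no percentage scale or ±5% reference is set, so no stated conclusion follows from them.
- **Nothing documents a systematic bias.** Section 6.1.2 says both packages use the same input and may differ through mesh and solver. Without a consistent shift, the share of plans over 5% is smaller (62% in the random example).
- **The objective is only to compare.** Sections 3.1.3 and 4.1.3 do not claim equivalence. A comparison is nevertheless hard to interpret without reference to the one tolerance the protocol states.

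A reader might infer that the CCC barely reacts to differences beyond 5%, so that excellent agreement would be reported while almost every DOSIE plan was overridden, whatever CCC threshold was used. The documents do not support that. It needs both a wide spread and a systematic shift, neither of which is documented. A strict threshold of 0.99 would also flag the 10% shift at CVs of 30%, 50% and 75% (0.948, 0.978, 0.988).

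**Conclusion.** The concern holds in this form: Section 12.1.4 does not measure agreement against the 5% tolerance in Section 6.1.2, and the CCC cannot stand in for it. For the same 10% shift the CCC runs from 0.35 to 0.99 over assumed CVs of 5% to 100%. Whether it would look reassuring or alarming for a given measure depends on a spread the documents do not report. The case of a high CCC with most plans over 5% is a possibility for widely spread measures under a systematic shift; it is not a prediction.

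The finding on the decision rule rests on reading the bound as belonging to the same CCC estimate, which is the natural reading. On that reading the rule has practically no ability to detect disagreement. Fiber intensity adds nothing to the comparison, because Section 6.1.2 sets it equal in both plans.

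This affects one secondary comparison in 18 patients. The primary response test is untouched. It is worth correcting because the remedy is cheap and the present analysis could mislead in either direction.

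**What to change.** Amend Section 12.1.4 as follows.

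1. For each computed measure, excluding fiber intensity, make the main summary the per-patient percentage difference between DOSIE and COMSOL. Report the mean and the Bland-Altman 95% limits of agreement, each with confidence intervals, against ±5%.
2. Report how many of the 18 plans exceed 5% on each measure, and how many were overridden under Section 6.1.2, with exact 95% confidence intervals. Precision will be modest: with 0 of 18 over the limit, the upper bound is 1 − 0.025^(1/18) = 18.5%.
3. State which measures trigger the override, and whether 5% is relative or in percentage points, so that Sections 6.1.2 and 12.1.4 use one definition.
4. Keep the CCC with its interval as a secondary description, and drop the rule that compares the estimate with its own lower bound.

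No new data are needed, since Section 6.1.2 already makes the comparison for each plan. The costs are a protocol and SAP wording change, the work of defining the 5% rule measure by measure, and the chance that reported agreement looks less favorable than a CCC would suggest.
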